 PK blood samples for AMG 994 and AMG 404 should be collected at the exact nominal time point relative to their respective end of infusions as noted above [see hours (relative to end of infusion) rows for AMG 994 and AMG 404]. If unable to collect a blood sample at the specified nominal time point, collect it as close as possible to the nominal time point and record the actual collection time. PK samples not collected at exact nominal time point will not be considered protocol deviations. For cycles 3+, AMG 404 PK samples should be collected at predose on day 1 of every cycle and at end of infusion at every other cycle on day 1 starting in cycle 3 (ie, day 1 of cycles 3, 5, 7 and so on).

 A tumor biopsy is required at baseline. Tumor tissue (archival within < 6 months of enrollment or recent acquisition) must be available for correlative studies. Subjects must consent to allow the acquisition of formalin-fixed paraffin-embedded (FFPE) material (block or unstained slides) by study personnel for performance of correlative tissue studies. Fresh tumor biopsies are required for subsequent time points. [REDACTED]

 Safety follow-up visit will occur 30 (+7) days and 140 days ( $\pm$ 1 week) after the last dose of AMG 994 and AMG 404 combination therapy.

 Long-term follow-up phone call at 6 months ( $\pm$ 1 week) after the last dose to collect information on adverse events, serious adverse events, concomitant medications, start of new therapies, and disease status. **After end of study, serious adverse events suspected to be related to investigational products that the investigator becomes aware of, will be reported to Amgen. As a study endpoint is overall survival, the investigator will also need to collect/report fatal serious adverse events (regardless of causality) to Amgen within 24 hours following the investigator's awareness of the event.**

 Physical exam is required on days [REDACTED] of each cycle. Height will be measured at screening only. Weight will be measured at screening and each study

AMG 404 to be administered on [REDACTED] after the end of infusion of AMG 994 if a  $\geq$  grade 2 infusion reaction is not observed. The dose is [REDACTED]

Product: AMG 994 and AMG 404

Protocol Number: 20190136

Date: 16 June 2022

Page 48 of 180

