#### **8.1.4 Long-term Follow-up**

Long-term follow-up phone call at 6 months ( $\pm 1$  week) after last dose of protocol required therapies to collect information on serious adverse events, survival, start of new therapies, and disease status.

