##### **8.2.4.1 Time Period and Frequency for Collecting and Reporting Safety Event Information**

###### **8.2.4.1.1 Adverse Events**

The adverse event grading scale to be used for this study will be the Common Terminology Criteria for Adverse Events (CTCAE) Version 5.0 and is described in Section 11.4.

The investigator is responsible for ensuring that all adverse events observed by the investigator or reported by the subject that occur after first dose of protocol-required therapies through the end of study are reported using the Events CRF.

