###### **8.2.4.1.2 Serious Adverse Events**

The investigator is responsible for ensuring that all serious adverse events observed by the investigator or reported by the subject that occur after signing of the informed consent through end of study visit are reported using the Events CRF.

All serious adverse events will be collected, recorded and reported to the sponsor or designee within 24 hours of the investigator's **awareness** of the event, as indicated in Section 11.4. The investigator will submit any updated serious adverse event data to the sponsor within 24 hours of it being available.

Since the criteria for the CTCAE grading scale differs from the regulatory criteria for serious adverse events, **if adverse events correspond to grade 4 CTCAE toxicity grading scale criteria (eg, laboratory abnormality reported as grade 4 without manifestation of life-threatening status), it will be left to the investigator's judgment to also report these abnormalities as serious adverse events. For any adverse event that applies to this situation, comprehensive documentation of the event's severity must be recorded in the subject medical records.**

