### 9.4.1 Planned Analyses

#### 9.4.1.1 Interim Analysis and Early Stopping Guidelines

Safety data will be reviewed on an ongoing basis. Based on accumulating safety data, BLRM will be used to make dosing recommendations. In DLRMs, Amgen, in consultation with the site investigators, will review the BLRM recommended dose level and will review all available cumulative data by cohort prior to making dose escalation recommendations. As a sensitivity analysis, a 1-parameter Continual Reassessment Method model may be used to estimate the dose-toxicity relationship and in particular to estimate the dose level with a 25% DLT rate in order to help make dose escalation decisions. Adverse events, including late onset immune-mediated toxicities, and DLTs observed in all subjects will be evaluated continually and fully integrated into all DLRMs and considered in all enrollment and dosing decisions. If during the study there is any grade 5 adverse event (or any 2 of the same grade 4 adverse events) at least possibly related to AMG 994 or AMG 404, further accrual will be suspended; Amgen will conduct a safety analysis and submit to the regulatory authority for review prior to resuming enrollment.

Given that a fixed-dose administration of AMG 404 [REDACTED] is used as part of the AMG 994 plus AMG 404 combination, the 2-parameter BLRM for single agent AMG 994 will be used. Key details of the BLRM model as used in this study are as follows. A bi-variate normal prior distribution (parameters "a" and "b") is used for the BLRM model with bi-variate normal prior are as follows: the mean natural log (ln) of "a"  $\ln(a) = [REDACTED]$ , SD of "a"  $SD(\ln(a)) = [REDACTED]$ , mean  $\ln(b) = [REDACTED]$ ,  $SD(\ln(b)) = [REDACTED]$  and correlation = [REDACTED]. The target toxicity probability interval (TPI) is defined as a rate at least [REDACTED] and less than [REDACTED]; an excessive or unacceptable TPI is a rate of [REDACTED] or higher. The prior distribution is specified such that probability of DLT is [REDACTED] for the starting dose [REDACTED] and [REDACTED] for the reference dose [REDACTED] where the probability that the true DLT rate is [REDACTED] at the lowest planned dose is [REDACTED] and the probability the true DLT rate is [REDACTED] at the reference dose is [REDACTED]. The BLRM will be used [REDACTED] to recommend the next dose level and at the end of dose [REDACTED]

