Subjects who are alive and have not progressed, whether on-study or lost to follow-up, will be censored at their last evaluable tumor assessment date. Censoring rules for progression-free survival analysis are given below in Table 5-1.

Safety Follow-Up (SFU)

A safety follow-up visit will be performed approximately 30 (+7) days and 140 days (\pm 1 week) days after the end of the last dose of AMG 994 and AMG 404 combination therapy.

Serious Adverse Event

A Serious Adverse Event is defined as any untoward medical occurrence that, meets at least 1 of the following serious criteria:

- Results in death (fatal)
- Immediately life-threatening
- Requires in-patient hospitalization or prolongation of existing hospitalization
- Results in persistent or significant disability/incapacity
- Other medically important serious event
- Is a congenital anomaly/birth defect

Study Day

Post study day: study day= (date - date of Study Day 1) + 1

Pre-study day: study day= (date – date of Study Day 1)

Study Day 1

It is defined as the first day that investigational product is administered to the subject. The day before Day 1 is referenced as Day -1.

Treatment-emergent Adverse Event (TEAE)

A treatment-emergent adverse event is any adverse event starting on or after the first administration of any study drug, as determined by the flag indicating if the adverse event started prior to the first dose on the Events CRF, and 140 days (\pm 1 week) after the last dose of AMG 994 or AMG 404 whichever is later. The severity of each adverse event will be graded using the CTCAE version 5.0. Adverse events will be coded using MedDRA v23.0 or later.

Treatment-emergent Treatment-related Adverse Event

A treatment-emergent treatment-related AE is any treatment-emergent AE that per investigator review has a reasonable possibility of being caused by the investigational product.

Time to Progression (TTP)

Time to progression is defined as time from the start of treatment until the disease starts to get worse or spread to other parts of the body.

$$\text{TTP (in months)} = (\text{Earliest date of disease progression, censor} - \text{Date of first dose} + 1)/30.4$$

Table 5-2. Censoring Rules for TTP

Situation	Date of Event or Censoring	Outcome
PD, no prior new anticancer therapy or prior to start of new anticancer therapy	PD	Event
No PD, no new anticancer treatment	Last visit; otherwise, first IP dose date	Censored

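### Drug-related events starting more than 140 days after last dose are collected but fall outside the SAP's only treatment-related AE definition, so related-AE incidence may be undercounted

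*SAP*

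**What the plan says.** **Definitions (SAP Section 5).** The start of the treatment-emergent window is set by a CRF flag and its end by a day count, in these words: "as determined by the flag indicating if the adverse event started prior to the first dose on the Events CRF, and 140 days". An allowance of one week either way is attached to that day count. The count is anchored to the final dose of whichever product was stopped second: "after the last dose of AMG 994 or AMG 404 whichever is later". A related event is then defined within that set: "A treatment-emergent treatment-related AE is any treatment-emergent AE that per investigator review has a reasonable possibility of being caused by the investigational product". The SAP gives no other definition of a treatment-related AE.

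**Collection (protocol).** Section 8.2.4.1.1 requires that AEs "that occur after first dose of protocol-required therapies through the end of study are reported using the Events CRF". Section 8.2.4.1.2 requires that SAEs "that occur after signing of the informed consent through end of study visit are reported using the Events CRF". Section 8.1.5 places end of study at the last scheduled long-term follow-up call, 6 months (± 1 week) after last dose. The long-term follow-up footnotes to Tables 1-3 and 1-5 have that call "after the last dose to collect information on adverse events, serious adverse events, concomitant medications, start of new therapies, and disease status". Section 8.1.4 describes the same call as "after last dose of protocol required therapies to collect information on serious adverse events, survival, start of new therapies, and disease status", without non-serious AEs.

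**Reporting.** SAP 9.6.2 lists six treatment-emergent tables and six tables under a treatment-related heading. Protocol 9.4.2.3.2 promises tables of fatal AEs, SAEs and AEs leading to withdrawal, with no treatment-emergent limit in their wording. SAP Section 10 declares no departures from the protocol's analyses.

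**The concern.** Treatment-emergent and treatment-related AEs are a primary endpoint in both documents. A time limit on all-cause events has a clear purpose: it keeps background disease and later therapy out of the count. That purpose is much weaker once the investigator has judged an event to be caused by the product. Because the SAP makes related events a subset of treatment-emergent ones, attribution to the drug cannot bring back an event that started after the window closed.

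The direction is one-sided. Leaving out first related events can lower the reported incidence or leave it unchanged, never raise it. The protocol's own safety review pays attention to this kind of event: "Adverse events, including late onset immune-mediated toxicities, and DLTs observed in all subjects will be evaluated continually".

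The wording adds a practical problem. Words such as *up to* are missing before the 140 days. The ± 1 week belongs to the safety visit and cannot be programmed as a cut-off, and the CRF flag settles only the start of the window. Two programmers could obtain different counts from the same data.

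**Working it through.** The plan states no figure on this point, so there is nothing to reproduce. The check is a trace of definitions followed by date arithmetic.

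**Step 1: follow one event through the text.** Take an event starting 160 days after the later last dose that the investigator judges related.
- *Collected?* Yes if serious (protocol 8.2.4.1.2). If not serious, yes under 8.2.4.1.1 and the Schedule footnotes, but 8.1.4 does not list it for the 6-month call.
- *Treatment-emergent?* No: 160 > 147, the latest reading of the window.
- *Treatment-related as the SAP defines it?* No, because it is not treatment-emergent.
- *In the SAP 9.6.2 treatment-emergent tables?* No. Every line of that block carries the restriction, including the SAE and fatal lines.
- *In the SAP 9.6.2 treatment-related tables?* Not if the Section 5 definition is applied. The titles of that block omit the words treatment-emergent.
- *In the protocol 9.4.2.3.2 tables?* If serious or fatal, apparently yes, since no limit is stated there.

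**Step 2: length of the uncovered interval.** Inputs: a cut-off of 140 days ± 7 (SAP Section 5), a call at 6 months ± 7 days (protocol 8.1.4), and 30.4 days per month (the SAP's own conversion).
- Nominal call day: 6 × 30.4 = 182.4
- Nominal interval: 182.4 − 140 = 42.4 days
- Shortest (late cut-off, early call): (182.4 − 7) − (140 + 7) = 175.4 − 147 = 28.4 days
- Longest (early cut-off, late call): (182.4 + 7) − (140 − 7) = 189.4 − 133 = 56.4 days
- Nominal share of post-dose follow-up: 42.4 / 182.4 = 23.2%

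**Step 3: number of events affected.** This equals the number of subjects still followed after the cut-off multiplied by their risk of a first related event in the interval. The documents give neither term, so no count follows from them.

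**The case against.** Several objections carry weight.

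- **The window is a legitimate choice.** Protocol Appendix 4 leaves the treatment-emergent definition to the SAP, and 140 days matches the second safety follow-up visit, after which there is only a phone call. This stands for all-cause events. It does not explain why an event already judged drug-related should be subject to the same limit.
- **The tables may not drop the event.** A reader might infer that late related events vanish from every AE table. The documents do not establish that. The related-block titles in SAP 9.6.2 omit treatment-emergent, and protocol 9.4.2.3.2 sets no limit on SAE and fatal-AE tables. What the texts show is a conflict.
- **Oversight is intact.** Both documents bring late-onset immune-mediated events into dose level review, and SAEs reach the sponsor within 24 hours of awareness. The gap is in reporting tables only.
- **Few subjects may be exposed to it.** A reader might infer that the interval is lost for every subject. Those who die, withdraw or are lost before the cut-off have no such interval, and entry requires only a life expectancy above 3 months. Late-onset events starting inside the window are still tabulated.
- **Late onset is not stated as expected.** A reader might infer that the plan expects these harms. Protocol 6.2.2.1 expects immune-mediated reactions with AMG 404 but says nothing about onset beyond 140 days. Section 9.4.1.1 says only that late-onset events will be evaluated.

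These points limit the size and reach of the problem but do not remove the mismatch between the definition and the collection period.

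**Conclusion.** The SAP's definition leaves out drug-related events starting in roughly the last 42 days (28 to 56) of post-dose follow-up, although the protocol collects events through that time. Following the definition can only lower reported related-AE incidence, and it conflicts with protocol 9.4.2.3.2 and with the SAP's statement of no changes.

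This rests on two readings: that the garbled treatment-emergent sentence means up to 140 days, and that the Section 5 definition governs the related tables in 9.6.2. For SAEs it does not depend on how the 6-month call is resolved. For non-serious AEs it does, because 8.1.4 and the Schedule footnotes disagree.

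The effect is a possible undercount among subjects followed long enough. A figure for missing subjects would need a late-onset rate and a follow-up fraction that the documents do not give, so none is offered. The trial is descriptive and dose level review is unaffected. This is a cheap improvement.

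**What to change.** In SAP Section 5:
1. State one fixed treatment-emergent cut-off without a visit window, for example up to and including 140 days after the later last dose.
2. Define a treatment-related AE as any AE from first dose through the subject's end of study that the investigator judges related, and use that definition for the treatment-related tables in 9.6.2.

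In SAP 9.6.2:

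3. Add a listing of all AEs and SAEs with onset after the treatment-emergent cut-off.

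In the protocol:

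4. Reconcile Section 8.1.4 with the footnotes to Tables 1-3 and 1-5 on whether the 6-month call collects non-serious AEs.

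The cost is SAP wording and one listing. The SAE data are already required; the non-serious data depend on item 4. Related-AE rates may become slightly less favourable. The SAP changes should be made before database lock.

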#### **8.1.3 Safety Follow-up**

Upon permanent discontinuation from the study treatment for any reason, a safety follow-up visit will be performed at 30 (+7) days and 140 days ( $\pm 1$  week) after the last dose of protocol required therapies. These visits include adverse event/serious adverse event assessment, a physical exam, blood work (chemistry; coagulation; complete blood count [CBC]; adrenocortiopic hormone [ACTH]; anti-neutrophil cytoplasmic antibodies [ANCA], anti-nuclear antibodies [ANA], pregnancy test), and urinalysis.

The chemistry includes albumin, alkaline phosphatase, ALT, AST, blood urea nitrogen (BUN)/total urea, calcium, chloride, creatinine, glucose, potassium, sodium, total bilirubin, total protein, thyroid stimulating hormone (TSH), and free T4.

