Radiographic response (Complete Response, Partial Response) requires confirmation by a repeat, consecutive scan at least 4 weeks after the first documentation of response and may be delayed until the next scheduled scan to avoid unnecessary procedures. Radiographic progression (Progressive Disease) requires confirmation by a repeat, consecutive assessment 4 to 6 weeks after the first detection of radiological progression. Upon discussion with the Sponsor, in the absence of clinical deterioration, subjects may continue to receive AMG 994 and AMG 404 combination treatment after confirmation of radiographic progressive disease as long as they continue to derive clinical benefit, until

clinical disease progression, or intolerance of study treatment, or clinically significant deterioration of health status requiring discontinuation, or the subject withdrawal of consent, whichever occurs first; or, in the absence of the above, up to 12 months if the subject achieves a complete response, and up to 24 months if partial response or stable disease.

If a subject discontinues treatment for reasons other than progression, tumor evaluations should continue according to the Schedule of Activities (see Section 1.3) until progression or start of a new treatment regimen.

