## 11.11 Appendix 11. Modified Response Evaluation Criteria in Solid Tumors Version 1.1 (Modified RECIST 1.1)

This study utilizes modified RECIST 1.1 criteria, which includes required confirmation of disease progression, and the following modification to RECIST 1.1:

- Up to 5 target lesions per organ and 10 total are allowed (compared to 2 per organ and 5 total for standard RECIST 1.1) to increase lesion sampling and reduce assessment error.

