No PD and new anticancer therapy or PD after start of new anticancer therapy	Last visit prior to new treatment; otherwise, first IP dose date	Censored
No PD, but death recorded	Date of death	Censored

Time to Subsequent Therapy

Time to subsequent therapy is defined as time from the start of treatment until the first subsequent therapy.

$$\text{TTST (in months)} = (\text{Earliest date of subsequent therapy, censor} - \text{Date of first dose} + 1)/30.4$$

Table 5-3. Censoring Rules for Time to subsequent therapy

Situation	Date of Event or Censoring	Outcome
No new anti-cancer therapy	Last visit; otherwise, first IP dose date	Censored
New anti-cancer therapy started	Start date of new anti-cancer therapy	Event

6. Analysis Sets

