9.5.2 Analyses of Secondary Efficacy Endpoint(s)

Listings of secondary efficacy endpoints will be produced for all subjects in the dose-escalation cohorts and the dose-expansion cohorts.

For all subjects in the Efficacy Analysis Set, the proportion of subjects and 95% CL with an objective response (complete or partial response per modified RECIST 1.1) will be tabulated by tumor type and planned dose level and schedule.

For all subjects in the Efficacy Analysis Set, Kaplan-Meier methods will be used to estimate the time of event curve, median time to event, and percentiles with 95% CI for

1) Duration of response (DOR, per modified RECIST 1.1),

2) Overall survival (OS)

3) Progression-free survival (PFS, per modified RECIST 1.1)

4) Time to progression (TTP, per modified RECIST 1.1) and

5) Time to subsequent therapy.

Kaplan-Meier methods will be used to estimate appropriate landmarks for DOR, OS, PFS and TTP (eg, 1-year PFS)

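### SAP Table 5-2 censors time to progression at the last visit or at death, so time without scans can count as progression-free

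*SAP*

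**What the plan says.** SAP Section 5, Table 5-2, has three censoring rows for TTP:

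- No progression and no new anticancer therapy: "Last visit; otherwise, first IP dose date".
- New anticancer therapy without earlier progression: "Last visit prior to new treatment; otherwise, first IP dose date".
- "No PD, but death recorded": the date of death.

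None of them names a tumor assessment. In the same section the PFS definition reads: "Subjects who are alive and have not progressed, whether on-study or lost to follow-up, will be censored at their last evaluable tumor assessment date".

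Both endpoints use progression per modified RECIST 1.1. SAP Section 9.5.2 plans Kaplan-Meier curves and medians, and adds: "Kaplan-Meier methods will be used to estimate appropriate landmarks for DOR, OS, PFS and TTP".

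On follow-up, Protocol Section 8.1.3 sets safety visits at 30 and 140 days after the last dose: "These visits include adverse event/serious adverse event assessment, a physical exam, blood work". Urinalysis is also listed; imaging is not. For subjects who stop treatment for a reason other than progression, Protocol Section 8.2.2 says "tumor evaluations should continue according to the Schedule of Activities", until progression or a new regimen.

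**The concern.** Progression under modified RECIST 1.1 is found on imaging. Once a scheduled scan has been missed, a later visit for blood work or a later death says nothing about whether the tumor had progressed by then. Table 5-2 nevertheless counts that time as progression-free follow-up.

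The subjects exposed are those who stop being scanned, or who die, without recorded progression. Appendix 11 of the protocol anticipates such cases when it describes stopping for symptomatic deterioration without objective progression.

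TTP and PFS should differ only in how they treat deaths. As written they also differ in how they treat missing scans, always in favor of TTP. A reader comparing the two curves could not separate the two causes.

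**Working it through.** **No stated figure to reproduce.** The documents give no TTP median, landmark or event count. The check is of direction first, then of size under assumed inputs.

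**Direction.** At a scan date with *d* progressions among *n* subjects at risk, the Kaplan-Meier factor is 1 − d/n. Censoring later adds *m* unscanned subjects to the risk set but no events, so the factor becomes 1 − d/(n + m), which is at least 1 − d/n. The events are the same under both rules, so the curve can only hold or rise.

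**Reference values (censoring at last scan).** Assumed: exponential progression time with a 90-day median, and scans every 56 days (the actual interval is redacted). Survival per scan interval is 2^(−56/90) = 0.650.

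- Day 183: the last scan is at day 168, so 2^(−168/90) = 0.274.
- Day 365: the last scan is at day 336, so 2^(−336/90) = 0.075.
- Estimated median: the curve is 0.650 at day 56 and 2^(−112/90) = 0.422 at day 112, so it reads 112 days.

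**Simulation of the Table 5-2 rule** (1,000,000 subjects per scenario). The time of stopping scans is exponential and independent of progression, tuned so that 5%, 15% or 30% stop without detected progression. Censoring is at a visit or death a fixed gap after stopping. The 6-month proportion, against 0.274 at last scan, is:

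| Stop scanning without PD | 30-day gap | 60-day gap | 140-day gap |
|---|---|---|---|
| 5% | 0.279 | 0.284 | 0.294 |
| 15% | 0.288 | 0.302 | 0.336 |
| 30% | 0.308 | 0.341 | 0.412 |

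- 12 months, 15% stopping: 0.083 (30 days) and 0.125 (140 days), against 0.075.
- The bias starts when a scheduled scan is missed. With 15% stopping and a last visit 55 days after the last scan there is no change; at 57 days the estimate is 0.301.
- The median stays at 112 days except with 30% stopping and gaps of 90 days or more, when it reads 168.
- With 15% stopping and a 140-day gap, varying the median from 60 to 150 days and the scan interval from 42 to 84 days, the 6-month estimate rises by 0.03 to 0.09.

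**Second simulation, on the protocol's visit pattern** (40,000 subjects per scenario). Safety visits are at 30 and 140 days. Assumed: true median 3 months, 10% per month stopping without progression, 8-weekly scans plus one at end of treatment, and median time to death 12 months.

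| Scanning after stopping | 6 months: Table 5-2 / last scan | 12 months: Table 5-2 / last scan |
|---|---|---|
| None | 0.396 / 0.248 | 0.190 / 0.058 |
| Half of subjects | 0.336 / 0.265 | 0.121 / 0.068 |
| All subjects | 0.279 / 0.278 | 0.077 / 0.076 |

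The true values are 0.249 and 0.062. Over all scenarios run (medians of 3 and 6 months, stopping at 5% to 20% per month), the rise was about 0 to 27 percentage points at 6 months and 0 to 31 at 12 months. Censoring at the last scan is not exact either: with 20% per month stopping and no later scans it gave 0.227 against 0.249 at 6 months, while the Table 5-2 rule gave 0.495.

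**The case against.** **The term is undefined.** The fallback to first dose date would have no use if *visit* meant any visit, because every analyzed subject was dosed and so has a day 1 visit. That suggests a tumor-assessment visit may have been meant. This stands as an ambiguity. But Table 5-3 uses the same phrase for time to subsequent therapy, which does not depend on imaging, and the date-of-death row cannot be read as a scan date.

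**The PFS comparison is incomplete.** The PFS sentence covers only subjects alive without progression. Death is a PFS event, so the death row has no PFS counterpart. The PFS rule for new therapy may be in Table 5-1, which is cited but is not in the text available for this review. This stands: strict agreement with PFS can be claimed for the first row only. The other two rows rest on the general point that unscanned time is not informative about progression.

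**Safeguards exist.** The protocol asks for scanning to continue, and with full compliance the effect disappears. SAP Section 6.1 also drops subjects with no on-study scan who are lost to follow-up or on study for less than 8 weeks. Neither removes subjects who were scanned and then stopped or died.

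**The size is assumed and modest.** This stands. The scan grid alone lifts the 6-month value from 2^(−183/90) = 0.244 to 0.274 under either rule. That 0.030 exceeds the added shift in every 5% scenario (0.005 to 0.020), and at 15% with 30- or 60-day gaps (0.014 and 0.028).

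**Conclusion.** The concern holds. Table 5-2 as written ties no TTP censoring date to a scan, and following it can only leave the curve and landmarks unchanged or raise them. The size cannot be fixed from the documents, because it depends on the scan interval, the rate of stopping without progression and compliance with scanning afterwards. In the first set of assumptions the 6-month shift runs from 0.005 (0.279 − 0.274) to 0.138 (0.412 − 0.274). In the second it runs from nearly nothing to 27 points.

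With 30 subjects per tumor type, the moderate shifts are within sampling error: the plan's own exact interval for a 20% rate is 8% to 39%. They are systematic, however, and do not average out. TTP is a descriptive secondary endpoint with no hypothesis test and no stopping rule attached, so reporting is affected and no trial decision is. The change is worth making before database lock, but it is not critical.

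**What to change.** In SAP Table 5-2:

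1. No progression, no new therapy: censor at the last evaluable tumor assessment.
2. New therapy without earlier progression: censor at the last evaluable tumor assessment before that therapy.
3. Death without progression: censor at the last evaluable tumor assessment.

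Keep first dose date as the fallback where there is no such assessment. If the sponsor prefers a different rule for any row, the SAP should define *last visit* and give the reason for departing from PFS.

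The same edit can settle a separate, smaller point. Appendix 11 describes criteria "which includes required confirmation of disease progression", yet ends duration of response at the first objective documentation of progression. Table 5-2 should state whether progression means first-detected or confirmed, and which date counts, consistently with PFS and duration of response.

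The cost is three table cells and the matching programming. No new data are needed. TTP estimates will be unchanged or less favorable.
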